9 CONTENT OF REPORTS

The results of this study will be presented in a standard BMS Clinical Study Report (CSR). Prior to completion of the CSR an Initial Data Assessment will be prepared briefly identifying the key results and any unanticipated findings that are unusual for a study within this program. Prior to completion of the Initial Data Assessment, a meeting for the Initial Data Assessment of study results will be held after database lock and unblinding. Attendees at this meeting will review efficacy and safety summaries and listings and will identify key results that should be highlighted in the Initial Data Assessment and CSR.

At the end of the study, when all subjects complete the follow-up period or discontinue prematurely, a final closeout report will be prepared. The reports will be mainly presenting safety summaries based on the OLE and the cumulative period. It will include the following summaries and the associated listings indicated in the respective sections in this analysis plan:

- Subject Disposition.
- Exposure summaries presented in [Section 7.4](#).
- Efficacy: Changes from baseline in UPCR and serum albumin.
- Adverse Events:
 - Serious adverse events (SAE).
 - AEs leading to study drug discontinuation.
 - AEs related to study drug.
 - Related events categorized by intensity.
 - Most common related AEs (reported in at least 2% of subjects in any treatment group).
 - AEs by intensity.
 - All AEs (serious or non-serious).
 - Most common (serious or non-serious) AEs (reported in at least 5% of subjects in any treatment group).
 - Serious adverse events and related serious adverse events with death as an outcome following EudraCT requirements.
 - Multiple AEs summaries including the required EudraCT summaries in [Section 7.6.4.1](#) (based on cumulative abatacept safety period).
- Laboratory Summaries:
 - Laboratory abnormalities.
 - Shift tables.
- Vital Signs based on OLE period only.
- Immunogenicity.
- Pharmacokinetics.

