4.5.2 Administration of Abatacept or Placebo

The Central Randomization System will confirm the subject's body weight and age and assign the number of vials of abatacept to allocate for the visit. Subjects will receive doses of study medication at every treatment period visit (Days 1, 15, 29, 57 and 85 during Double Blind Period).

Subjects who are randomized to receive placebo will be given either Dextrose 5% in Water (D5W) or Normal Saline (NS) at the discretion of the investigator. Placebo (NS or D5W) will be supplied by the investigative site.

A ± 3 day window is allowed for the dose on Day 15, a -3 and +7 day window is allowed for the dose on Day 29 and a ± 7 day window is allowed for doses thereafter. Infusions should occur at approximately the same time of day throughout the duration of the study.

All doses of study medication will be administered intravenously in a fixed volume of 100 ml at a constant rate of flow over approximately 30 minutes. Please flush with D5W or NS at the end of the infusion to ensure that the administration line used to deliver the drug solution is adequately cleared; please refer to the infusion set's manufacturer's materials to determine the appropriate flush volume needed to assure delivery of the entire dosage. The infusion solution must be prepared by a qualified staff member and supplied to personnel administering the dose in a container not identifying the contents so as to maintain the blind. The infusion of the fully diluted abatacept/placebo must be completed within 24 hours of reconstitution of the vials. The fully diluted abatacept/placebo may be stored at room temperature or refrigerated at 2°C to 8°C (36°F to 46°F) before use. The fully diluted solution should be discarded if not administered within 24 hours.

All intravenous infusions will be with the subject in the seated position. No adjustments will be made in treatment dose level or schedule. Subjects will be observed for adverse events and vital signs (seated blood pressure, heart rate, and temperature) from the start of each infusion (pre-dose and 60 minutes). There is a ± 5 -minute window for vital sign collection. Subjects will be observed for a minimum of 1 hour from the start of the infusion. The observation period should be extended if clinically indicated.

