4.5.4.2 Dose Modifications Due to an Adverse Event

If there is evidence of toxicity in abnormal laboratory tests or clinical adverse events that, in the judgment of the Investigator, could place the subject at increased risk, study drug administration should be interrupted and the investigator should notify BMS. Subjects may be considered eligible to receive further study medication treatment only if full resolution of the adverse event is documented. Under no circumstances should the dose of study drug be altered due to an adverse event.

The IV infusion dosing window may be extended if the delay is due to an adverse event and if the adverse event has completely resolved. For Day 15, the dose may be delayed up to 7 days. For all subsequent IV infusions, the dose may be delayed up to 14 days. If the adverse event has not resolved within these windows, the IV infusion scheduled for that visit should be skipped (missed one IV dose). For example, if the Day 57 dose could not be administered until the 73rd day, the Day 57 dose should be skipped and the subject's next dose would occur at the Day 85 visit. Only two missed doses are allowed in the Double Blind Period.

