- Double-blind period analysis: This analysis will be performed for the double-blind period when all subjects complete their Day 113 visit assessment or discontinue prematurely prior to Day 113. At the time of the first analysis the data will be unblinded. This analysis will include primary endpoint and secondary endpoints.
- End of study analysis: A second analysis will be performed at the end of the study when all subjects complete their open label extension (OLE) and follow-up period or discontinue prematurely.

This statistical analysis plan will describe the analysis to be performed at the end of the double-blind period and at the end of the study.

Prior to Protocol Amendment 2, the study design had a blinded-study drug period that was twice as long as the current double-blind period and was divided into 2 periods of equal length, known as Period 1 and Period 2, so that randomized subjects could switch blinded therapy. The current design eliminates Period 2 and renames the previous Period 1 as the double-blind period.

This modification does not impact the primary nor secondary study objectives. It does impact the exploratory objectives which addressed persistence of response and onset of response during Period 2, these are now eliminated.

For subjects who completed Period 1 and entered Period 2 prior to the protocol revision, the Period 1 data will be analyzed as part of the double-blind period since study execution during this timeframe is unchanged, the Period 2 data will only be listed. Period 2 data won't be part of any summaries except for safety summaries at the end of the study on the cumulative abatacept safety period.

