2 STUDY DESCRIPTION

2.1 Study Design

This is a phase II randomized, placebo-controlled, double-blind, parallel arm design study to evaluate the efficacy and safety of intravenous abatacept in treatment resistant nephrotic syndrome (Focal Segmental Glomerulosclerosis / Minimal Change) in adult and pediatric subjects.

This pilot study will randomize approximately 90 subjects 1:1 to intravenous (IV) abatacept or placebo in a double-blind (DB) fashion. The randomization will be stratified by Genotype for whom test results, obtained either prior to enrollment or at screening, are available (APOL1 high risk group vs. Others) and Age (< 18 y and ≥ 18 y).

The trial will consist of 4 periods: the screening period will be 28 days (can be extended an additional 14 days to complete testing by repeating screening labs), a 16 week double-blind treatment period (parallel arms: IV abatacept vs. IV placebo), a 168 day abatacept open label extension period (OLE), and a 6 month follow-up period.

Subjects randomized to abatacept treatment in the double-blind period will be dosed as follows. Adults will use the weight-tiered dose: < 60kg: 500mg, 60 to 100kg: 750mg, > 100kg: 1000mg;

pediatric patients 6 to 17 years who weigh < 75kg will receive:10mg/kg and those who weigh \geq 75kg will follow adult dosing. Dosing is on Day 1, 15, 29, 57, 85. Subject in the placebo arm will receive normal Saline or D5W following the same dosing schedule. In the OLE, subjects who enter will all receive age and weight-based IV abatacept every 28 days for 169 days.

The primary efficacy assessment, renal response (defined in [Section 8.1.1](#)), will be on Day 113. On Day 113, all subjects who choose to receive open label therapy with abatacept will enter the OLE. During the OLE, the durability (i.e., continuity of response) and stability (i.e., the change in urine protein/creatinine ratio (UPCR)) of response will be determined by continuing to capture and describe the same study outcomes among responders. Adjustment of background therapy will also be allowed during the OLE at the discretion of the investigators and subjects to determine the relative contribution (or need) of these agents for renal responses.

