2.3 Blinding and Unblinding

The subjects and clinical assessor(s) are not aware of which treatment is being administered to the subjects enrolled in the study. The pharmacist (or qualified drug preparation person) will be unblinded to study medication (abatacept or placebo).

The pharmacist (or qualified drug preparation person) will know the scheduled assignments and prepare the appropriate dose of active - abatacept or placebo accordingly. The prepared drug must be supplied to study personnel in a manner such that neither study personnel nor subjects will be aware of whether they receive active drug or placebo.

Blinding is critical to the integrity of this clinical drug trial. However, in the event of a medical emergency or pregnancy in an individual subject, in which knowledge of the investigational product is critical to the subject's management, the blind for that subject may be broken by the treating physician.

Before breaking the blind of an individual subject's blinded treatment, the Investigator should determine that the information is necessary, i.e., that it will alter the subject's immediate management. In many cases, particularly when the emergency is clearly not investigational product-related, the problem may be properly managed by assuming that the subject is receiving active product without the need for unblinding.

BMS personnel will be blinded to treatment assignment until all subjects have completed Day 113 and the database is locked for primary analysis.

The following individuals will have access to the treatment code during the study:

- As described in the DMC Charter, the members of the independent data monitoring committee (DMC) and the external reporting statistician will be partially unblinded with a right to fully unblind treatment codes if necessary to enable review of the emerging data.
- Personnel charged with generating and maintaining randomization files, packaging study medication, and operating the IVRS will also have access to treatment codes.

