6 STUDY PERIODS, TREATMENT REGIMENS AND POPULATIONS FOR ANALYSES

6.1 Study Periods

In this study, there are four study periods: screening period, double-blind period (DB), open label extension period (OLE), and follow-up period.

The following analysis periods defined below are for analysis purposes. The definitions below indicate the data to be included in the analysis of each specified period. Subjects discontinued during a specified period (DB or OLE) will be considered on-treatment for 56 and 42 days after the last dosing in that period for safety and efficacy analysis respectively. Follow-up period data will be included in one of the analysis periods depending on the time of completing the study.

Screening Period: Starts with the day of enrolment and ends prior or on the day of first dose of study medication (abatacept or placebo).

Double-Blind Period: Starts with the first dosing of double-blind study medication and ends 56/42 days (for safety/efficacy analysis) after the last dose of the double-blind period or the first dosing of OLE, whichever is earlier.

For subjects who completed Period 1 and entered Period 2 prior to Protocol Amendment 2, includes data from first dose date in Period 1 up to the first dose in Period 2.

Open Label Extension Period (OLE): Starts with the first dosing in the OLE and ends 56/42 (for safety/efficacy analysis) days after the last dose in the OLE.

Cumulative Abatacept Safety Period: Starts at the time of the first dose of abatacept (either in the double-blind period for the subjects randomized to abatacept or in the OLE for the subjects randomized to placebo) and continues up to 56 days post last dose of abatacept for safety (AE and laboratory summaries). The last abatacept dose can be last dose in double-blind period for subjects not treated in the OLE.

For subjects who completed Period 1 and entered Period 2 prior to the protocol revision:

- For subjects on abatacept during Period 1:
 - For subjects who do not enter OLE period: starts with the first dosing of Period 1 and ends 56 days after the last dosing of Period 1.
 - For subjects who enter OLE period: starts with the first dosing of Period 1 and ends 56 days after the last dosing of Period 1 combined with OLE period that starts with the first dosing in the OLE period and ends 56 days after the last dosing in the OLE period.
- For subjects on placebo during Period 1:

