APPENDIX 3 CLINICAL REPORTS CONTENT

Table 9-2: Safety Analysis by Period

	End of Double-Blind	End of Study	
	Period CSR	CSR	
	Double-Blind Period	Cumulative Abatacept Safety Period	OLE Period
Serious Adverse Events	X	X	X
AEs leading to study drug discontinuation	X	X	X
AEs related to study drug	X	X	X
Related events categorized by intensity	X	X	X
Most common related AEs (reported in at least 2% of subjects in any treatment group)	X	X	X
All AEs (serious or non-serious)	X	X	X
AEs by intensity	X	X	X
Most common (serious or non-serious) AEs (reported in at least 5% of subjects in any treatment group)	X	X	X
Serious adverse events and related serious adverse events with death as an outcome (EudraCT)		X	
AEs of Special Interest (Renal Related Events, Infections, Malignancy, Autoimmune Disorder, Infusional Reactions)	X	X	
Multiple Adverse Events	X	X	
EudraCT summaries - Exposure adjusted summaries		X	
Laboratory abnormalities	X	X	X
Laboratory Shift Tables	X	X	X
Mean Change from Baseline in Lab Parameters	X		
Vital Signs	X		X
Immunogenicity	X	X

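### The plan does not guarantee that the 56-day double-blind safety window has closed when its only double-blind safety summary tables are produced

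*SAP*

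**What the plan says.** - **Trigger.** The SAP's Schedule of Analyses runs the double-blind analysis "when all subjects complete their Day 113 visit assessment or discontinue prematurely prior to Day 113".
- **Lock.** SAP 2.3 states: "BMS personnel will be blinded to treatment assignment until all subjects have completed Day 113 and the database is locked for primary analysis". No cut-off date, minimum lag or later refresh of the double-blind tables is given.
- **Safety window.** Under SAP 6.1 the double-blind period "ends 56/42 days (for safety/efficacy analysis) after the last dose of the double-blind period or the first dosing of OLE, whichever is earlier". SAP 7.6.3 uses the same 56-day limit for incidence rates.
- **Reports.** In SAP Appendix 3, Table 9-2, the double-blind column sits under the end-of-double-blind report only. The end-of-study report has an OLE column and one headed "Cumulative Abatacept Safety Period". By SAP 6.1 the latter begins with a subject's first abatacept dose.
- **Closeout.** SAP Section 9 says: "At the end of the study, when all subjects complete the follow-up period or discontinue prematurely, a final closeout report will be prepared". It describes the content as mainly OLE and cumulative-period safety.
- **Exposure.** SAP 7.4.1 credits every subject who does not continue into the OLE with 56 days beyond the last double-blind dose, without truncation at lock.

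**The concern.** The SAP chooses a 56-day window deliberately, then schedules the tables that use it at a point that may fall inside the window. Subjects who enter the OLE are unaffected, because their double-blind period ends at the first OLE dose. The same holds for those who moved into the former Period 2. What remains is the subject who stays out of the OLE and was last dosed less than 56 days before lock.

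Two things are at stake. First, the arm-by-arm double-blind table is the only randomised safety comparison in the trial, and it could go out incomplete by the SAP's own definition with no planned update. Second, what happens to a late event depends on the arm. On abatacept it is picked up by the cumulative period. On placebo, with no abatacept ever given, it belongs to neither end-of-study period and reaches no summary table.

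**Working it through.** **1. The plan's own figure.** SAP 7.4.1 justifies 56 days as two dosing cycles and about four half-lives. Two cycles: 2 × 28 = 56. Protocol 3.3.1 equates five half-lives with 70 days, so one is 70 / 5 = 14 days and four are 4 × 14 = 56. The figure reproduces.

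**2. When the window closes.** SAP 2.1: "Dosing is on Day 1, 15, 29, 57, 85". Protocol 4.5.2: "a ± 7 day window is allowed for doses thereafter". Protocol 4.5.4.2, for adverse events: "For all subsequent IV infusions, the dose may be delayed up to 14 days". For a subject not entering the OLE, closing day = last dose day + 56:

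| Last double-blind dose | Window closes | Days after nominal Day 113 |
|---|---|---|
| Day 78 (85 − 7) | Day 134 | 21 |
| Day 85 (on schedule) | Day 141 | 28 |
| Day 92 (85 + 7) | Day 148 | 35 |
| Day 99 (85 + 14, adverse-event delay) | Day 155 | 42 |

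If the last trigger event is a discontinuation shortly after an infusion, nearly all 56 days can still be open.

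**3. When late events are collected.** Protocol Table 5.1-4 places the first off-drug follow-up visit, with adverse-event monitoring, 56 days after the last dose, ± 14 days. For an on-schedule completer that is Day 127 to Day 155, after the trigger.

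**4. Exposure credited against time observed.** For the on-schedule completer, SAP 7.4.1 gives (85 − 1 + 1) + 56 = 141 days. With data only to Day 113, 141 − 113 = 28 days are credited but unobserved, and 28 / 141 = 20%. If the rates in SAP 7.6.3 and 7.6.4 use this exposure, that subject contributes event-free time that nobody observed.

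**5. How many subjects.** Accrual and OLE uptake are not in the documents, so these are assumptions, with zero lag to lock.
- At 2 to 5 subjects reaching Day 113 per 28 days and 10% to 40% staying out of the OLE: 2 × 0.10 = 0.2 to 5 × 0.40 = 2.0 in both arms, so 0.1 to 1.0 on placebo under 1:1 allocation.
- With 45 placebo subjects accrued uniformly over 1 to 3 years: 45 × 0.10 × 28 / 1095 = 0.1 to 45 × 0.40 × 28 / 365 = 1.4 on placebo. The upper end implies faster accrual than the first calculation: 90 × 28 / 365 = 6.9 per 28 days.
- A 14-day lag with data used to lock halves these figures. A lag of 28 days brings them to zero for on-schedule completers.

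Recent early discontinuations would add to these counts. One subject is 1 / 45 = 2.2 percentage points of an arm, and moves a row by that much only if not already counted in it.

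**The case against.** The strongest reply is that the SAP gives a trigger for the analysis, not a data cut-off. If lock follows the last Day 113 visit by 28 days or more and data to lock are used, the gap closes for an on-schedule completer. That is right, and it limits the point to a missing guarantee: nothing in the plan requires such a lag.

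Some text points towards including late data. SAP 6.1 says follow-up data will be placed in one of the analysis periods. SAP 7.6 names the double-blind period among those summarised. The word mainly in Section 9 leaves room for other tables. But Table 9-2 is the specific text and gives the final report no double-blind column. Its split header was read from a PDF, though Section 9 agrees with this reading.

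A reader might infer that late placebo events are lost, or that the double-blind comparison is biased against abatacept. The documents support neither. SAP 7.6.1 lists all reported adverse events, and SAP 7.6.2 lists events of interest up to database lock. Within the double-blind table both arms are truncated by the same rule. The asymmetry lies only in what the final report later adds, and its cumulative column is abatacept-only by design, not an arm comparison. SAP 7.6 also plans no testing of adverse-event frequencies.

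It is also tempting to say that the affected subjects are those most likely to have adverse events. Nothing in the documents shows this, and early stoppers last dosed more than 56 days before lock have closed windows.

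**Conclusion.** The point holds as a gap in the reporting schedule, not as a demonstrated loss of data. The SAP defines a 56-day window, credits it in full as exposure, and produces the double-blind summaries once, at a time when the window may still be open. The shortfall is up to 28 days for an on-schedule completer outside the OLE, up to 42 days past nominal Day 113 after a permitted delay, and nearly 56 days for a discontinuation at the trigger.

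The number affected is probably about 0 to 2 subjects in total and 0 to 1 on placebo (1.4 on placebo at the least favourable assumptions tried). This rests on assumed accrual, assumed OLE uptake and zero lag to lock. The primary efficacy analysis is untouched. The priority is low, but the change is specific and cheap.

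**What to change.** In SAP Table 9-2 and Section 9, add a Double-Blind Period column to the end-of-study report for serious adverse events, adverse events leading to discontinuation, all adverse events, adverse events of special interest, exposure-adjusted rates and laboratory abnormalities. Run it on the full SAP 6.1 window. Present it as an update beside the first-lock tables, with differences footnoted. It should not replace them, because the added data will have been handled after the sponsor is unblinded.

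Alternatively, state a data cut-off for double-blind safety at 56 days after the last double-blind dose for subjects not entering the OLE. The first report's safety tables would then wait for the last such window to close.

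The first option costs one re-run of existing programs and small count differences between the two reports.

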APPENDIX 1 DOCUMENT HISTORY

Table 9-1: Document History

Version	Statistician	Date	Notes/Revisions
1.0	[REDACTED]	16 January 2018	Original version
2.0	[REDACTED]	13 September 2018	Incorporates Protocol Amendment 2 - Period 2 is eliminated and the previous Period 1 is renamed as the double-blind period. - [REDACTED] - For subjects who completed Period 1 and entered Period 2 prior to the protocol revision, the Period 1 is analyzed as part of the double-blind, the Period 2 data are only listed. Period 2 data are not part of any summaries except for safety summaries at the end of the study on the cumulative abatacept safety period.

APPENDIX 2 RELEVANT PROTOCOL DEVIATIONS

Pre Randomization:

- UPCR < 2.7 at screening.
- eGFR below the following level at screening:
 - 50 for subjects < 18 years (new Schwartz equation).
 - 50 for subjects ≥ 18 years (CKD-EPI equation).
- Body mass index (BMI): > 45 in subjects ≥ 18 years of age and ≥ 99% percentile for subjects < 18 years of age at screening.
- Hemoglobin (Hgb) < 7.0g/dl at screening.
- White Blood Count (WBC) < 2,000/mm³ (2 x 10⁹/L) at screening.
- Platelets < 75,000/mm³ (75 x 10⁹/L) at screening.
- Serum ALT or AST > 3 times upper limit of normal at screening.
- Subjects systemically using any of CS (low dose, prednisone or equivalent at doses ≤ 15mg/day), calcineurin inhibitors (cyclosporine and tacrolimus), MMF and MPA for treatment of TRNS (use for other medical indications [e.g. asthma] is allowed), satisfying any of the following:
 - Started using one of the above agents within 8 weeks of enrollment.
 - Not using the standard dose or
 - Have not been on stable dose for at least 4 weeks prior to randomization.

Post Randomization:

- FSGS or MCD diagnosis not confirmed by a pathology report.
- Use of prohibited medication:
 - Any systemic immunosuppressive or immunomodulator per protocol including, but not limited to cyclophosphamide, methotrexate, belimumab, azathioprine, leflunomide, rituximab, experimental therapies, everolimus, sirolimus, corticotropin injection gel (ACTH) or plasmapheresis.
 - Combined use of two or more renin-angiotensin system (RAS) inhibitors.
- Missed two or more doses of investigational product for any reason during double-blind period.

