3.3.1 Inclusion Criteria

1. Signed Written Informed Consent

- a) Prior to study participation, written informed consent from subjects, or in the case of minors (< 18 years), written permission (informed consent) from parents, guardians, or legally acceptable representatives must be obtained according to local laws and regulations.
- b) Assent from minor subjects should be obtained per local requirements.

2. Target Population

- a) Subjects diagnosed with TRNS (FSGS/MCD).
 - i) Pathological findings of either FSGS (excluding collapsing FSGS) or MCD on the most recent renal biopsy (renal biopsies will not be part of this study). This will be confirmed by review of the pathology report (not slides) by a central pathologist. The criteria for pathology review are in [Appendix 1](#).
 - ii) UPCR ≥ 3 at screening.

iii) Treatment Resistant or Treatment Intolerant

(1) Treatment resistant is defined as persistence of UPCR ≥ 3 in spite of therapy with any one of the following agents: corticosteroids (CS), calcineurin inhibitors (cyclosporine and tacrolimus), sirolimus, mycophenolate mofetil (MMF), mycophenolic acid (MPA), or cyclophosphamide.

(a) Duration of therapy: The duration of CS therapy required to determine treatment resistance will be 6 weeks in subjects < 18 year of age and 12 weeks for subjects ≥ 18 years. For all other agents, the minimum duration of therapy will be 16 weeks, regardless of age.

(2) Intolerance to any 2 of these agents, regardless of duration of treatment or age.

b) Subjects must be receiving either an angiotensin-converting-enzyme inhibitor (ACEi) or an angiotensin receptor blocker (ARB) or have intolerance documented in the source documents maintained at the site. If a subject is currently receiving an ACEi or ARB, the dose must be stable for at least 2 weeks, prior to randomization. Combined use of renin-angiotensin system (RAS) inhibitors will not be allowed. If aldosterone inhibitors (spiro lactone or eplerenone) or aliskiren (direct renin inhibitor) are used, they must also be at stable doses.

c) A minimal level of renal function at screening based on estimated glomerular filtration rate (eGFR) will be required.

i) ≥ 45 for subjects < 18 years (new Schwartz equation).⁴⁸

ii) ≥ 45 for subjects ≥ 18 years (CKD-EPI equation).⁴⁷

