d) **APOLI genotyping**: Subjects will be genotyped for the *APOLI* renal risk variants SNPs [Risk allele G1 (rs73885319 and rs60910145) and risk allele G2 (rs71785313)]. Subjects with 2 copies of the high-risk *APOLI* variants are in the *APOLI* high-risk group which will be used for stratification at randomization. Genotyping during screening will not be necessary if results of previous testing are available. Subjects will be allowed to opt-out of genotyping for *APOLI*. Subjects who refuse genotyping will still be eligible to be randomized.

e) **Concomitant Medication**:

i) Subjects may enroll with or without the following background agents used to treat TRNS (FSGS/MCD):

(1) CS (low dose, prednisone or equivalent at doses ≤ 10 mg/day)

(2) calcineurin inhibitors (cyclosporine and tacrolimus)

(3) MMF

(4) MPA

ii) Agents must be used at standard doses, must not have been started within 8 weeks of enrollment

iii) Agents must be **stable for at least 4 weeks prior to randomization**.

- iv) No adjustment in doses of concomitant medications will be allowed during the double-blind period other than for dose reductions or holds to address drug-related toxicity.
- f) Subjects who had previously been treated with rituximab are allowed in the study if use had occurred more than 6 months prior to randomization and there are laboratory results indicating the presence of circulating B cells (CD19+).
- g) Hypertension must be controlled and stable. Hypertension control is defined as a blood pressure (BP) \leq 140/90 for subjects \geq 18 years of age and $<$ 95th percentile for subjects $<$ 18 year of age by gender, age and height percentile.⁴⁹
- h) Changes in diuretic use should be avoided prior to the Day 113 assessment unless necessary to manage an adverse event.
- i) Treatment to manage dyslipidemia is allowed. HMG CoA reductase (hydroxymethylglutaryl CoA reductase) inhibitors or statins use must be stable 2 weeks prior to randomization and throughout the treatment periods.
- j) Subject Re-enrollment: This study permits the re-enrollment of a subject that has discontinued the study as a pre-treatment failure (ie, subject has not been randomized / has not been treated). If re-enrolled, the subject must be re-consented.

3. Age and Reproductive Status

- a) Males and Females, ages \geq 6 years.

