7.2 Study Conduct

Relevant protocol deviations, which could have major impact on the interpretation of the primary efficacy endpoint of the study results, will be identified prior to the unblinding the database for all subjects who are randomized and receive double-blind medication. Relevant protocol deviation criteria are listed in [APPENDIX 1](#).

All relevant protocol deviations, pre-randomization and during double-blind period, will be listed and summarized by treatment arm. The per-protocol analysis population will exclude subjects with at least 1 relevant protocol deviation. Relevant protocol deviations will not be assessed for the OLE analysis.

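### SAP Appendix 2 counts a screening eGFR below 50 as a relevant protocol deviation although the protocol admits 45 and above, and the SAP is unclear whether screening deviations affect the per-protocol set

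*SAP*

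**What the plan says.** **Entry.** Protocol 3.3.1 item 2c sets the screening eGFR minimum by age group: "≥ 45 for subjects < 18 years (new Schwartz equation" and "≥ 45 for subjects ≥ 18 years (CKD-EPI equation". The synopsis and Protocol 3.1 give the same figure.

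**Deviation list.** The pre-randomization part of SAP Appendix 2 counts a subject as a relevant deviator if screening eGFR is below a stated level. The two levels are "50 for subjects < 18 years (new Schwartz equation" and "50 for subjects ≥ 18 years (CKD-EPI equation". The equations match those of the entry criterion.

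**Use of the list.** SAP 7.2 states: "All relevant protocol deviations, pre-randomization and during double-blind period, will be listed and summarized by treatment arm". It continues: "The per-protocol analysis population will exclude subjects with at least 1 relevant protocol deviation". SAP 7.5 repeats the primary analysis in the per-protocol population when more than 10% of either arm meets a deviation criterion. Neither section limits this to deviations after randomization.

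**The narrower wording.** SAP 6.3.3 and Protocol 8.2 define the per-protocol population by removing subjects whose relevant deviations arise within the 16-week double-blind period. Both then state the 10% trigger without repeating that limit.

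**The concern.** A protocol deviation is a departure from the protocol. A subject with a screening eGFR of 45 to below 50 has not departed from it on this item, yet the SAP classes that subject as a relevant deviator. SAP 7.2 describes relevant deviations as ones that could seriously affect how the primary result is read, so the label carries weight in the report. The list is meant to be programmed, so the cut-off will be applied as written unless someone changes it.

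Two things are at stake:

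- The deviation listing and the by-arm summary would overstate non-adherence to entry criteria.
- If screening items count for the per-protocol set, eligible subjects could help trigger that analysis and then be removed from it. Whether they count is itself unsettled, and the same question applies to every pre-randomization item in the appendix.

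**Working it through.** **1. The overlap.** Entry requires eGFR ≥ 45, and the deviation flag is eGFR < 50. Both hold for 45 ≤ eGFR < 50, a band 5 units wide in each age group.

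**2. Is 50 a tolerance margin?** A tolerance would make the flag looser than entry, so that small breaches are ignored. The table divides each SAP Appendix 2 cut-off by the limit in Protocol 3.3.1 or 3.3.2. For a minimum, a ratio below 1 is looser; for a maximum, a ratio above 1 is looser.

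| Item | Type | Entry limit | SAP flag | Ratio | Flag against entry |
|---|---|---|---|---|---|
| UPCR | minimum | 3 | 2.7 | 0.90 | looser |
| Haemoglobin (g/dl) | minimum | 8.5 | 7.0 | 0.82 | looser |
| Platelets (per mm³) | minimum | 100,000 | 75,000 | 0.75 | looser |
| WBC (per mm³) | minimum | 3,000 | 2,000 | 0.67 | looser |
| ALT/AST (× ULN) | maximum | 2 | 3 | 1.50 | looser |
| BMI, adult | maximum | 40 | 45 | 1.125 | looser |
| BMI, paediatric (percentile) | maximum | 99th | 99th | 1.00 | equal |
| **eGFR, both age groups** | **minimum** | **45** | **50** | **1.11** | **stricter** |

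The laboratory and BMI limits are looser or equal in every row except eGFR, which is 11% stricter (50/45 = 1.111).

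**3. Other lines that flag permitted subjects.** Protocol 5.2.7 lets a subject with a high screening BMI enrol at the investigator's discretion, provided oedema explains the BMI and it was not known to be raised at disease onset. The BMI lines in SAP Appendix 2 carry no such exception. A child at or above the 99th percentile, or an adult above 45, who was enrolled properly under 5.2.7 would also be flagged.

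**4. Which rule governs the per-protocol set?**

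- *SAP 7.2 and 7.5:* one relevant deviation of any timing excludes the subject and counts towards the trigger.
- *SAP 6.3.3 and Protocol 8.2:* a screening eGFR flag is not a deviation within the double-blind period, so it excludes nobody. Whether it counts towards the trigger is not stated.

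**5. Size of the trigger.** The plan has 90 subjects randomized 1:1, or 45 per arm. That number reproduces: 40% against 12% at two-sided 5% and 80% power needs 45 per arm with a continuity correction. For the trigger, 4/45 = 8.9% does not exceed 10% and 5/45 = 11.1% does, so 5 subjects in one arm are enough. This assumes that all 45 are treated.

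**6. What cannot be computed.** The documents give no distribution of screening eGFR. The number of subjects at 45 to below 50 is therefore unknown and could be zero.

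**The case against.** The strongest objection is that little depends on this. The primary and secondary efficacy analyses use the intent-to-treat population. The per-protocol analysis only repeats the primary one, and only above the 10% trigger. Under the sections that define the population, SAP 6.3.3 and Protocol 8.2, a screening flag excludes nobody. Protocol 8.2 also has the list approved before database lock, which leaves a point at which to correct it. All of this stands and limits the weight of the finding. It does not make the cut-off right, because no other section reconciles 50 with 45.

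A reader might infer more than the documents support:

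- *That eligible subjects will be dropped from the per-protocol analysis.* This follows only on the SAP 7.2 and 7.5 reading, and only if the analysis is triggered.
- *That the treatment comparison is biased.* The flag uses a value from before randomization and is the same in both arms.
- *That eGFR is the only line that flags permitted subjects.* It is the only stricter numeric cut-off, but the BMI lines also do so by omitting the oedema exception.
- *That the steroid line is another loosened limit.* The SAP has "CS (low dose, prednisone or equivalent at doses ≤ 15mg/day" and the protocol has "CS (low dose, prednisone or equivalent at doses ≤ 10 mg/day". In SAP Appendix 2, however, the dose only describes which users the start-date, standard-dose and stability rules cover. No line makes exceeding it a deviation, so it is not evidence for the pattern in the table.
- *That 50 survives from an earlier entry criterion.* Amendment 1 (17 April 2017) lowered the paediatric minimum, and both SAP versions (16 January and 13 September 2018) came later. The previous minimum is not given, and the logged change names only subjects under 18, so a carry-over cannot be confirmed.

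**Conclusion.** The inconsistency is real and covers both age groups. As written, any subject at 45 to below 50 who met the entry criterion would be reported by arm as a relevant deviator. A deliberate tolerance does not account for it, because eGFR is the one numeric cut-off set tighter than entry.

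The timing conflict is a second, separate defect and would remain if the eGFR lines were corrected. Until it is settled, per-protocol membership, and possibly whether that analysis is run at all, depends on which section is followed.

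The effect is confined to the deviation listing and summary and, on the SAP 7.2 and 7.5 reading, to the conditional per-protocol repeat. It does not reach the intent-to-treat results. The conclusion rests on the two thresholds and on the wording of the four sections, not on any assumed number of affected subjects. It should be corrected, mainly because correction is cheap and a change after unblinding could look data-driven.

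**What to change.** Before unblinding:

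1. Reconcile both eGFR lines in SAP Appendix 2 with the protocol entry criterion, so that no subject who met the criterion in force at enrolment is flagged.
2. Reconcile the BMI lines with the oedema exception in Protocol 5.2.7.
3. Align SAP 6.3.3 with SAP 7.2 and 7.5 by stating whether a pre-randomization deviation excludes a subject from the per-protocol set, and whether it counts towards the 10% trigger. Check the result against Protocol 8.2.
4. In the same edit, correct the cross-references in SAP 6.3.3 and 7.2, which send the reader to Appendix 1 for a list that is in Appendix 2.

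The cost is a few lines of SAP text and a rerun of the deviation listing. Data collection, trial conduct, sample size and the intent-to-treat analyses do not change.
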